**1. Introduction and Purpose:**

Recently there has been an explosion of new minimally invasive technologies for the management of postmenopausal vulvovaginal symptoms, vaginal wall laxity, sexual dysfunction, and even mild to moderate urinary incontinence with very limited scientific studies to back the merits of these technologies and their claims.

**Goals:**

1. To evaluate the efficacy of radiofrequency (RF) and hybrid fractional laser (HFL) treatment for vaginal rejuvenation [REDACTED]

[REDACTED]  
[REDACTED]  
[REDACTED]  
[REDACTED]  
[REDACTED]

2. To establish objective methods to monitor vaginal rejuvenation following treatments by optimizing biopsy sample size and histological/gene expression methods.

**Hypothesis:**

We hypothesize that it is possible that vaginal rejuvenation via RF or HFL treatment could be a placebo effect. There are claims of improvement in urinary incontinence, appearance, and an array of vulvovaginal symptoms. To date, there is a paucity of objective data to support these

claims. We are unaware of any long-term studies following the outcomes after treatment.

## 2. Background:

Vaginal rejuvenation is a catch-all term of trendy procedures which claim to provide relief of many issues affecting women's health, ranging from postmenopausal vulvovaginal symptoms (i.e. dryness, burning, itching), stress urinary incontinence, sexual dysfunction or discomfort, vaginal laxity, and labial appearance, amongst others. 3,4

1. Alinsod, R.M. Transcutaneous Temperature Controlled Radiofrequency for Orgasmic

### **3. Concise Summary of Project:**

This is a single-center, randomized, prospective study designed to evaluate the efficacy of radiofrequency and hybrid fractional laser for vaginal rejuvenation. [REDACTED]

[REDACTED]

[REDACTED]

[REDACTED]

[REDACTED]

[REDACTED]

[REDACTED]

A series of eight horizontal black bars of varying lengths, decreasing from left to right. The bars are evenly spaced and extend across the width of the frame.

#### 4. Study Procedures:

A series of six horizontal black bars of varying lengths, decreasing from top to bottom. The bars are evenly spaced and extend across the width of the frame.

The purpose of the study and specific inclusion and exclusion criteria and potential risks/benefits will be discussed with the potential study subject. All interested subjects will be given the Consent Form with adequate time for review. The Investigator and/or his designee will address questions and concerns raised by the subject. Those subjects who elect to participate will sign the Consent Forms prior to any study procedures.

## Treatment Groups

*IntraGen:* █ patients will each undergo a three-part treatment of the vulvovaginal area. █

*IntraGen Placebo:* █ patients will undergo a three-part placebo treatment, space 1 month apart (+/- 10 days) of the vulvovaginal area. █

[figure not shown]
DiVa: █ patients will undergo a three-part treatment, spaced 1 month apart (+/- 10 days) of the vulvovaginal area. █

DiVa Placebo: █ patients will undergo a three-part placebo treatment, spaced 1 month apart (+/- 10 days) of the vulvovaginal area. █

[figure not shown]
All

[figure not shown]
Each patient will undergo testing at baseline and will be followed conservatively with no further therapy until they reach 6 months (+/- 10 days) █

[figure not shown]
█ Those in the treatment group will be followed to 9 months (+/- 10 days) after the initiation of treatment with appropriate analysis. Those in the placebo group will be provided 3 monthly treatments with both █ RF and █ HFL .These post placebo dual therapy patients will be conservatively followed with no further treatment until they reach 6 months (+/- 10 days) after the initiation of the dual █ RF and █ HFL treatments. 6 months (+/- 10 days) post dual therapy they will return for subjective and objective testing. These patients will return for 9 month visit (+/- 10 days) after the initiation of dual therapy. P █

[figure not shown]

#### Visit Timelines

[figure not shown]
[figure not shown]
[figure not shown]

Figure 1: Zimmern Probe

### **Primary outcome measure:**

### 1) Improvement in Vulvovaginal Symptoms

- The Vulvovaginal Symptoms Questionnaire is a validated questionnaire which was created to study vulvovaginal symptoms in postmenopausal women including their discomfort, emotions, life-impact and sexual-impact. [REDACTED]

## 2) Perceived changes in vaginal laxity

- This will be measured by both biometric probe analysis for elasticity and subjective questionnaire: the Vaginal Laxity Questionnaire (VLQ)

### **Secondary outcome measures**

Perceived changes in urinary incontinence

- This will be measured by subjective questionnaire: Urogenital Distress Short Form (UDI-6) and Incontinence Impact Questionnaire Short Form (IIQ-7)

Perceived improvement in sexual dysfunction

- This will be measured by subjective questionnaire: Female Sexual Function Index (FSFI)

### **5. Sub-Study Procedures: None**

### **6. Criteria for Inclusion of Subjects:**

Women should be between 40 and 65 years of age

Women should be post-menopausal

Women should be amenorrheic for at least 12 months

Postmenopausal women presenting with one or more of the following:

- Vulvar itching
- Vulvar burning or stinging
- Vulvar Pain
- Vulvar irritation
- Vulvar dryness
- Discharge from subject's vulva or vagina
- Odor from subject's vulva or vagina

## **7. Criteria for Exclusion of Subjects:**

- Unable to commit to future appointments within one year
- Planning on moving away from Dallas within one year
- History of other energy-based vaginal therapy within one year
- Vaginal hormone replacement therapy must have a one month washout period prior to treatment and discontinued use for duration of study, systemic replacement is not excluded
- Prior labiaplasty, or vaginal injections of fat or fillers within 6 months
- Prior anti-incontinence surgery in the last 12 months
- Urinary incontinence requiring more than 2 pads/day
- Clinically significant pelvic organ prolapse (POP)
- Urinary tract infection in the past 3 months
- Unstable diabetes
- Ongoing chemotherapy
- Immunodeficiency status (steroid intake, ongoing chemotherapy)
- Diffuse pain syndrome or chronic pain requiring daily narcotics
- Chronic vaginitis including bacterial vaginosis, HPV, herpes, or other active STI
- Recent abnormal Papanicolaou test result
- Recent abnormal pelvic exam (i.e. concerning lesions)
- Vulvar dermatologic pathology requiring local steroid use
- Undiagnosed abnormal genital bleeding
- If less than two years postmenopausal, not using a medically approved method of contraception (i.e. oral, transdermal, implanted contraceptives, intrauterine device, diaphragm, condom, etc.)
- Pregnancy
- History of genital fistula or a thin rectovaginal septum
- Uncontrolled psychiatric conditions (well-controlled depression/anxiety is not excluded)

- Body Mass Index > 35
- Actively participating in or planning on participating in pelvic floor muscle strengthening exercise
- Presence of pacemaker, AICD, or other electrical health maintenance device

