#### **8. Sources of Research Material:**

Medical history and demographic data (age, ethnicity, BMI, gravidity parity (both current and past), menopausal status, hysterectomy/ovarian status, allergies, current medications, major illnesses/hospitalizations, previous surgeries, smoking status, systemic hormone replacement therapy (HRT), current sexual activity, and medical co-morbidities). Subjective assessments including Vulvovaginal Symptom Questionnaire, Female Sexual Function Index, Vaginal Laxity Questionnaire, Urogenital Distress Inventory Short Form, and Incontinence Impact Questionnaire Short Form. Objective assessments including Zimmern Probe measurement and vulvovaginal biopsy studies for histology and gene expression studies.

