**14. Biostatistics:**

The primary outcome of this study is the VSQ. We have estimated the standard deviation to be 2.5 based on prediction of pre-treatment scores ranging from 4 to 14. To detect a difference of 3 points on this measure with 80% power, 20 subjects per group will be required.

One way analysis of variance will be used for comparison of groups both for the VSQ and the Q-PCR data. Questionnaire results will be compared by comparing the results at each time point compared to pretreatment assessment.

UT Southwestern affiliated clinical statisticians have been and will continue to be consulted throughout the statistical analysis process.

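### The one-way ANOVA of the VSQ leaves out the baseline score; a prespecified ANCOVA would gain precision at no cost, with systemic hormone use at most a minor extra covariate

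*Combined protocol and SAP*

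**What the plan says.** Section 7 (exclusion criteria) requires a one-month washout of vaginal hormone therapy and keeps it stopped, but permits systemic therapy: "discontinued use for duration of study, systemic replacement is not excluded". Section 8 lists systemic therapy as a separate item among the history and demographic data: "smoking status, systemic hormone replacement therapy (HRT), current sexual activity".

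Section 14 (Biostatistics) gives the analysis in two sentences. The first is "One way analysis of variance will be used for comparison of groups both for the VSQ and the Q-PCR data". The second is "Questionnaire results will be compared by comparing the results at each time point compared to pretreatment assessment". The visible text names no covariate and no adjusted or sensitivity analysis. It does not say whether the ANOVA is run on raw scores or on change from baseline.

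Section 14 sizes the trial at 20 per group for a 3-point VSQ difference with 80% power. On the SD it says: "We have estimated the standard deviation to be 2.5 based on prediction of pre-treatment scores ranging from 4 to 14". The arm sizes under Treatment Groups in section 4 are blacked out, so 20 per arm is taken from section 14.

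**The concern.** A one-way ANOVA has a single factor, the arm. The baseline value of the primary outcome, usually the best predictor of the follow-up value, does not enter as a covariate. Systemic hormone use does not enter either, although the protocol controls the vaginal route and so treats at least local hormone exposure as relevant.

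With about 20 women per arm, an active arm and its placebo can differ by chance on either variable. The unexplained variance also widens every interval. This matters because the Hypothesis section asks whether the apparent benefit could be a placebo effect. The answer rests on each active arm against its own placebo, and a tighter interval for that contrast is worth having.

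**Working it through.** **The plan's own figure.** The SD of 2.5 equals the predicted range divided by four: (14 − 4)/4. Alpha is not stated; I assume 0.05 two-sided. For two groups, n = 2 × (1.96 + 0.84)² × (2.5/3)² ≈ 10.9, so 11 per group (12 by exact t-test). A four-group one-way ANOVA with means 0, 1.5, 1.5 and 3 needs 17. The stated 20 therefore does not follow from the stated inputs alone, but it errs on the safe side. At 20 per arm, unadjusted power is 96.7% pairwise (normal approximation) and 88.8% for that four-group ANOVA.

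**Validity.** In simulation with hormone use affecting the VSQ (30% users, 2 points; 50% users, 3 points), the type I error of the unadjusted four-group ANOVA was 4.9% and 5.1%.

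**Assumptions for the rest.** The documents give no prevalence of systemic hormone use, no effect of it on the VSQ and no baseline to follow-up correlation. I take prevalence p = 0.3, user/non-user difference g = 1 or 2 points (stable over time) and within-group correlation ρ = 0.5 or 0.7. I also assume that the SD of 2.5 (variance 6.25) holds at follow-up.

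**Chance imbalance.** With binomial draws of 20 per arm, an active arm and its placebo differ by 4 or more users with probability 23% at p = 0.3 (16% at 0.2, 26% at 0.4). A difference of 4 users shifts the unadjusted raw-score contrast by (4/20) × g, which is 0.2 points at g = 1 and 0.4 at g = 2. The standard error of that contrast is 2.5 × √(2/20) = 0.79 and the target is 3 points.

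**Hormone use as the only covariate.** Its share of the variance is p(1 − p)g²/6.25: 0.21/6.25 = 3.4% at g = 1 and 0.84/6.25 = 13.4% at g = 2.

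**Hormone use added to baseline VSQ.** Let B = p(1 − p)g² and W = 6.25 − B. The overall correlation is r = (B + ρW)/6.25. Residual variance is 6.25(1 − r²) with baseline VSQ alone and W(1 − ρ²) with both covariates.

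| g | ρ | r | Baseline VSQ only | Reduction from 6.25 | Both | Further reduction |
|---|---|---|---|---|---|---|
| 1 | 0.5 | 0.517 | 4.58 | 27% | 4.53 | 1.1% |
| 1 | 0.7 | 0.710 | 3.10 | 50% | 3.08 | 0.6% |
| 2 | 0.5 | 0.567 | 4.24 | 32% | 4.06 | 4.3% |
| 2 | 0.7 | 0.740 | 2.82 | 55% | 2.76 | 2.3% |

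Baseline VSQ alone takes the standard error of a pairwise contrast from 0.79 to between 0.68 and 0.53. Adding hormone use then changes it by 0.014 at most (0.651 to 0.637 at g = 2, ρ = 0.5). Baseline adjustment also absorbs much of a hormone imbalance: at g = 2 and ρ = 0.5, the 0.4-point shift falls to about 0.4 × (1 − 0.567) = 0.17.

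**Degrees of freedom.** With 80 women in four arms, the residual degrees of freedom go from 76 to 75 with baseline VSQ and to 74 with hormone use as well. One degree in 75 is 1.3%, about the size of the whole hormone gain at g = 1.

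**The case against.** The strongest reply is that nothing here is wrong. Randomisation makes the unadjusted test valid, chance imbalance is already part of its standard error, and power for 3 points is ample. All of that stands. A reader might infer that allowing systemic hormones biases the comparison or inflates the false-positive rate. The documents do not support this: the trial is randomised, and the simulated error rate stays near 5%.

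A reader might also infer that adjusting for hormone use would remove about 13% of the variance. That figure needs a 2-point effect and a model without baseline VSQ. The documents give no effect of systemic hormones at all. Section 7 restricts the vaginal route and expressly permits the systemic one, which is weak evidence that systemic use predicts the VSQ. Section 8 also lists age, BMI and smoking among other candidates, and nothing ranks hormone use above them. So hormone use is at most optional.

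Third, section 14 compares each time point with pretreatment. If the ANOVA is run on change scores, a stable hormone effect on level cancels and baseline is partly used. The text does not say that it is. Even then the variance of change, 2W(1 − ρ), is 5.41 at g = 2, ρ = 0.5 and 3.25 at ρ = 0.7, against 4.24 and 2.82 for ANCOVA on baseline alone. The case for ANCOVA remains, though the gain is smaller.

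Finally, text beside the randomisation statement in section 3 is redacted, so stratification by hormone use cannot be ruled out. The analysis as stated would still lack the term.

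**Conclusion.** The point holds as a free improvement. The planned VSQ analysis is valid but less precise than the collected data allow. Baseline VSQ would remove about 27% to 55% of the raw-score variance if the within-group correlation is 0.5 to 0.7. Systemic hormone use would remove roughly a further 1% to 4% of the residual variance, given 30% users and a 1 to 2 point difference. These inputs are assumptions, and 20 per arm is read from section 14. The gain is in interval width and in robustness to chance imbalance. It does not rescue power, which is adequate for the 3-point target without adjustment.

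**What to change.** In section 14, for the VSQ only, replace the one-way ANOVA with a prespecified ANCOVA of month-6 VSQ on arm and baseline VSQ, reporting each active arm against its own placebo. Month 6 suits this because, under Treatment Groups, the placebo women go on to dual therapy and the randomised comparison with placebo is then no longer available. Optionally name baseline systemic hormone use (yes/no) as a second covariate, decided before any outcome data are seen, and state that it is recorded at baseline. Keep the unadjusted result as a sensitivity analysis. Leave the Q-PCR analysis as stated.

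The cost is a few lines of wording, one residual degree of freedom for baseline VSQ and one more if hormone use is added. No new data or visits are needed, and eligibility does not change.

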#### **8. Sources of Research Material:**

Medical history and demographic data (age, ethnicity, BMI, gravidity parity (both current and past), menopausal status, hysterectomy/ovarian status, allergies, current medications, major illnesses/hospitalizations, previous surgeries, smoking status, systemic hormone replacement therapy (HRT), current sexual activity, and medical co-morbidities). Subjective assessments including Vulvovaginal Symptom Questionnaire, Female Sexual Function Index, Vaginal Laxity Questionnaire, Urogenital Distress Inventory Short Form, and Incontinence Impact Questionnaire Short Form. Objective assessments including Zimmern Probe measurement and vulvovaginal biopsy studies for histology and gene expression studies.

#### **9. Recruitment Methods and Consenting Process:**

[REDACTED]

[REDACTED]

[REDACTED]

[REDACTED]

[REDACTED]

[REDACTED]

[REDACTED]

[REDACTED]

At the time of their recruitment, subjects will be notified of the risks and benefits of the study and will be provided with the consent form for their consideration. Informed consent and HIPAA Authorization will be done in the presence of the principal investigator, co-investigators or designated clinical trial coordinator under the University of Texas Southwestern Medical Center at Dallas guidelines. A copy of the signed consent and HIPAA Authorization will be given to the subject, and the original will be kept in the source documents. All subjects will be

repeatedly asked if they have any questions regarding the study procedures.

#### **10. Potential Risks:**

The risks of radiofrequency, high frequency laser treatment, and dual therapy administering both radiofrequency and a high frequency laser of the vulvovaginal region include discomfort, mild edema, temporary erythema, spot bleeding, potential for transient over-active bladder, injury to bowel and bladder, and painful intercourse due to over-treatment. Less commonly, scarring, burns, and infection could occur. Should infection occur, treatment with antibiotics and even surgical intervention (i.e. I&D) may be required.

The risks of vaginal wall punch biopsy include pain, bleeding, bruising, infection, and possible scarring.

The RF or HFL treatment procedure will be performed by a medical provider who has been trained by [REDACTED] in the application of the device. The punch biopsy and probe application will be performed by this same doctor. There is no known risks associated with the suction probe to measure the anterior biomechanical vaginal wall tissue properties in situ.

There is also a potential risk of Loss of Confidentiality during data collection. However, this risk can be minimized by de-identification of the patient data, and access limited to members of the research team.

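### Section 14 states no placebo comparison for UDI-6 or FSFI, the scales nearest two harms named in Section 10, and no count of women who worsen on any scale

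*Combined protocol and SAP*

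**What the plan says.** Section 10 lists risks of radiofrequency, laser and dual therapy, among them "potential for transient over-active bladder, injury to bowel and bladder, and painful intercourse due to over-treatment".

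The outcome measures in Section 4 include instruments in related domains. The first primary outcome is headed "Improvement in Vulvovaginal Symptoms" and uses the VSQ, described as covering "vulvovaginal symptoms in postmenopausal women including their discomfort, emotions, life-impact and sexual-impact". UDI-6 and IIQ-7 come under "Perceived changes in urinary incontinence", and FSFI under "Perceived improvement in sexual dysfunction". Section 8 confirms that all of these are collected.

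Section 14, which shows no redaction mark, gives two analyses. The first is "One way analysis of variance will be used for comparison of groups both for the VSQ and the Q-PCR data". The second sets questionnaire results at each time point against the pretreatment assessment. It states no other comparison and no count of women who deteriorate.

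Under Treatment Groups, Section 4 describes a placebo arm for each device. It also says that placebo women are later given three monthly treatments with both devices.

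**The concern.** The Hypothesis in Section 1 is that any effect of these devices may be a placebo effect. The same reasoning applies to harm: a change from baseline on UDI-6 or FSFI mixes the effect of the device with everything else that happens to these women over six months. The placebo arms exist to separate the two, but for these scales Section 14 does not use them.

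A comparison of means raises a second, smaller problem. It nets women who get worse against women who get better. If a device helps most women and causes painful intercourse or discomfort in a few, the VSQ means can still favour it, and nothing in Section 14 would bring out the few.

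At stake is whether the trial can say anything placebo-controlled about two symptom harms that its own risk section names, using scores it already collects.

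**Working it through.** **Inputs.** From Section 14: VSQ standard deviation 2.5, difference 3 points, power 80%, 20 per group. Assumed, because the documents do not give them: two-sided alpha 0.05, individual changes, test-retest correlation and deterioration rates. Arm sizes in Section 4 are redacted, so 20 per arm is taken from Section 14.

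**The plan's own figure.** The normal formula for two means gives n = 2 × (1.960 + 0.842)² × (2.5/3)² = 10.9, so 11 per group. A t-test needs 12, a four-group F test with least favourable means 17, and a t-test with Bonferroni correction for six pairs 19. The stated 20 is not reproduced exactly, but alpha, correction and dropout are not stated, and 20 is conservative under each of these. The difference does not bear on this point.

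**Which comparison each scale gets in Section 14.**
- VSQ: between groups (ANOVA) and against pretreatment.
- UDI-6, IIQ-7, FSFI and VLQ: against pretreatment only.

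Write the change in an active arm as background change plus device effect. The pretreatment comparison estimates the sum; only active minus placebo estimates the device effect. If background improvement equals device harm, the pretreatment comparison shows zero.

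**What a mean can hide (assumed changes).**
- 18 women improve by 4 and 2 worsen by 6: mean improvement (18×4 − 2×6)/20 = 60/20 = 3.0.
- SD of those changes: √[(18×1² + 2×9²)/19] = √(180/19) = 3.1.
- Against a placebo arm with mean change 0 and SD 2.5: t = 3.0/√(9.47/20 + 6.25/20) = 3.4, p about 0.002.
- A second case, 85% improving by 4 and 15% worsening by 3: 0.85×4 − 0.15×3 = 2.95. In simulation with 20 per arm and SD 2.5, a two-group t-test declares benefit about 82% of the time.

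**Why a count must be read against placebo.** With no true change, the SD of a difference of two scores is 2.5 × √[2(1 − r)]. The chance of worsening by 3 or more points (normal approximation) is:
- r = 0.7: SD 1.94, 3/1.94 = 1.55, about 6%.
- r = 0.5: SD 2.50, 3/2.50 = 1.20, about 12%.
- r = 0.3: SD 2.96, 3/2.96 = 1.01, about 16%.

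In an arm of 20 that is 20 × 0.06 = 1.2 to 20 × 0.16 = 3.2 women by chance alone.

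**Precision of a count at 20 per arm.**
- 0 of 20: exact 95% upper limit 1 − 0.025^(1/20) = 16.8%.
- 3 of 20: exact 95% interval 3% to 38%.
- Fisher power for 20% against 5% (assumed rates): 17% at 20 v 20, and 41% if 40 v 40 could be pooled.

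**The case against.** The strongest reply is that the primary outcome is already compared with placebo. A reader might infer that harm is never compared with placebo. The documents do not support that: the VSQ ANOVA compares groups, is not directional, and would show a mean worsening. A reader might also infer that all outcomes are worded as benefit. Only the VSQ and FSFI headings are. Laxity appears as "Perceived changes in vaginal laxity" and the urinary outcome as "Perceived changes in urinary incontinence", and no heading makes a test one-sided.

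Nor can it be said that adverse events go unrecorded or uncompared. Section 11 is redacted after its first sentence, and much of Section 4 is redacted too. Section 8 lists research material, and its silence on events proves little. The documents describe no harm count over the whole study, so the later dual therapy in placebo women is a reason to fix the time point of a comparison, not an error already made.

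Other limits also stand. Bowel or bladder injury, burns and scarring are clinical events, not scale scores. The documents give no item content for UDI-6 or FSFI, so the link to over-active bladder and painful intercourse is inferred from the stated domains. The 3-point VSQ difference is a group target, not a criterion for individual deterioration. Section 10 calls the over-active bladder transient, so it may have resolved by 6 months. Finally, this is a pilot, and any mean-based analysis nets gains against losses.

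None of this supplies a placebo comparison for UDI-6 and FSFI. One may call that an efficacy gap, but the same omission leaves worsening on those scales uncontrolled.

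**Conclusion.** The point holds within Section 14 as published. UDI-6 and FSFI have no stated comparison with placebo, although placebo arms exist and these are the scales nearest two named harms. No scale has a stated count of women who worsen. The first gap is the more important, because it gives up the randomised contrast; the second is a matter of reporting.

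The netting example shows what is possible, not what is likely. Its individual changes are invented, and its 3.0 equals the between-group target only if the placebo change is zero. Ten per cent worsening in one arm also lies within the 6% to 16% that chance could produce at a 3-point cut, so a count has meaning only beside the placebo count.

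**What to change.** In Section 14:

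1. State a between-arm comparison, active against placebo, of change from baseline in UDI-6 and FSFI at the 6-month visit, before placebo women begin dual therapy. The visible part of Section 4 suggests this order, but the text around it is redacted, so Section 14 should state the time point itself.
2. As a descriptive supplement, report by randomised arm the number of women who worsen on VSQ, UDI-6 and FSFI. Fix a justified threshold for each scale in advance. Give exact 95% intervals and the active-minus-placebo difference, and say that the counts are to be read only against placebo.

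The cost is a paragraph and a few tables from questionnaires already collected, with no new visit or measurement. The drawbacks are wide intervals at 20 per arm, no powered test of harm, and a 6-month score that may miss transient symptoms. The report should state these limits, including the 16.8% upper limit when no one worsens, and should not present a zero count as absence of harm.
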